4.2.2. Secondary Efficacy Endpoints

1. Proportion of subjects reporting improvement in their MBS other than a headache, 2 hours post-treatment initiation (if rescue therapy was not used), in their first eligible treated migraine attack. MBS may be nausea, photophobia, phonophobia as defined by each subject prior to beginning of the treatment.
2. Proportion of subjects reporting reduction of migraine headache pain 1-hour post treatment initiation (if rescue therapy was not used), from severe or moderate to mild or no pain, or from mild to no pain, in their first eligible treated migraine attack.
3. Proportion of subjects who are pain free at 2 hours post treatment initiation (if rescue therapy was not used), in their first eligible treated migraine attack.

4.2.3. Safety Endpoint

Safety of the study device following study treatment: Rate of Adverse events related or unrelated to the study device [Time Frame: 24 hours post treatment initiation].

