8.1. Schedule of Events

The schedule of events is depicted in **Table 1** and **Figure 1**.

Table 1: Schedule of Events

Visit	Visit 1	Run-In Period	Visit 2	Self-Practice Period	Visit 3	Treatment Period	Visit 4
Event / Timeline	Day -28	-28 +10 days from Visit 1	Day 0	up to Day 14	remote; Up to Day 14	Up to 5 episodes / Day 70+10	Up to 5 episodes / Day 70+10
Written Informed Consent	X						
Eligibility assessment	X		X				
3-month migraine retrospective history questionnaire	X						
Medical history & Demography	X						
Prophylactic anti-migraine & rescue headache medication	X			X ¹			X ¹
Physical examination ² & Vital signs	X						
Documented significant change in health status (e.g., surgery, accident, MI)			X				
Pregnancy test ³	X		X				
Run-in Diary		X					
Enrollment & Randomization			X				
Device and PRO ⁴ training			X				
Device and PRO Self-practice			X	X			
Blinding assessment questionnaire			X				
Device logs and PRO verification			X ⁵		X		X
Active / sham treatment						X	
Diary PRO at baseline, 1, 2 & 24 hr post treatment						X	
Global Impression of Effect questionnaire							X
Adverse events			X				X
End of study							X

1 Document change in medications

2 Physical exam to include: Head, eyes, ears, nose, throat (HEENT), Lungs, Heart and Neurologic exam; Vital signs include blood pressure, pulse and respiratory rate

3 Pregnancy test for women of childbearing potential only

4 PRO: Patient Reported Outcome

5 Device logs only at Visit 2

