8.1.3. Visit 2 - Randomization (28+10 days from Visit 1)

Written below are the assessments to be completed at Visit 2:

- Review of Run-in Diary.
- Change in prophylactic anti-migraine & rescue headache medication will be documented.
- Documented significant change in health status (e.g., surgery, accident, MI)
- Pregnancy test (women of childbearing potential only).
- Verification of eligibility.
- Randomization to Group A (Active Treatment) and Group B (Sham Control).
- Subject will read the User manual and watch the instructional video and be trained on the device by the study team.
- Device size will be adjusted to subject head circumferences.

 Neurolief Brain Innovation	THE RIME STUDY: ABRIDGED CLINICAL INVESTIGATION PLAN	Doc No.: CL-CIP-001 Abridged Ref Rev: REV.2 / 11JUN2019 Pg. 25 of 41
--	---	--

- Subject will self-practice the device along with the mobile application to become familiar with its use and with the stimulation.
- Blinding Assessment questionnaire.
- Subject will be trained on the Patient Reported Outcome (electronic/hard copy) diary for documenting the outcome measures and rescue medication intake.
- Mobile application/Device logs verification for stimulation intensity. Stimulation intensity to be above 2mA. In case subject fail to reach a minimum stimulation intensity of 2mA, subject will be withdrawn.
- Subject will be provided with the device, a dedicated smartphone, a subject's instruction form and Patient Reported Outcome diary (electronic/hard copy) for up to 14 days Self-Practice period at their home.
- Adverse events occurring during the visit will be documented.

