8.1.5. Visit 3 (remotely or clinic visit; up to day 14)

Written below are the assessments to be completed at Visit 3:

- A visit is needed in case device logs were not download to the study cloud-based database, otherwise a remote contact is allowed.
- Upon subject notification of the completeness of 2 self-practice sessions:
 - Study team will confirm within device logs that the subject completed at least one self-practice session successfully. Device logs shall present Subject's study code, Device serial number, Date of stimulation session, stimulation session timeline bar presenting stimulation events such as "pass", "fail", Device failure events. A stimulation session marked as "Pass" if a minimal stimulation of 2 mA was delivered, or "Fail" if a minimal stimulation of 2 mA was not delivered. An eligible self-practice session will be defined by a recorded device log with a stimulation duration of at least 30 minutes of a "Pass" session in the device log.
 - Study team will verify correct reporting on PRO and inform/retrain subject on correct PRO reporting, if required.
 - If at least one self-practice session completed successfully, study team will contact the subject and guide him/her to use the device during up to 5 migraine episodes within up to day 70+10 from Visit 2.
 - Call will be documented and will be considered as remote study Visit 3.

- If both self-practice sessions are non-eligible, subject will be withdrawn from the study. Study team will call the subject and invite him/her to a study termination visit. Subject invitation will be considered as remote study Visit 3, termination visit will be documented.

8.1.6. Treatment period (up to 5 treated Migraine episodes or day 70±10 whichever comes first)

- Subjects will use the device for at least 1 and up to 5 migraine episodes within up to day 70±10 from visit 2, whichever comes first.
- Subjects will be instructed to differentiate between 2 different Migraine episodes which will be defined by, at minimum, 48 hours free of pain in between.
- Study team will contact the subject periodically to remind him/her to use the device during his/her next migraine episode.
- Study team will periodically verify device logs of treated attacks on the study cloud database and may contact the subject for re-training if required.
- Subject will use the device at home or surroundings immediately upon the initiation of the Migraine headache and no later than 30 minutes afterwards:

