- Subjects will be asked to refrain from consuming rescue medication/cannabis for at least 2 hours post treatment initiation. Subjects using rescue medication/cannabis prior to 2 hours post treatment initiation will be considered as failure (will be assigned the value of 0=no headache pain reduction) in the primary analysis.
- Subjects will document on the Patient Reported Outcome diary:
 - Pain according to a 4 points scale (0=no pain, 1=Mild pain, 2=Moderate pain, 3=Severe pain) at 1 and 2 hours \pm 30 minutes and at 24 hours \pm 6 hours post initiation of treatment.
 - Most Bothersome migraine-associated Symptom (MBS) other than a headache (chosen at baseline) improvement (yes/no) at 1 and 2 hours \pm 30 minutes post-treatment initiation.
 - Rescue medication intake.

8.1.7. Visit 4 - Termination visit (following 5 treated Migraine episodes or day 70 \pm 10, whichever comes first)

Written below are the assessments to be completed at Visit 4:

- After up to 5 migraine episodes within up to day 70 \pm 10, whichever comes first, subject will report to the clinic and return the device, Smartphone and hard copy subject diary, if applicable.
- Change in prophylactic anti-migraine & rescue headache medication will be documented.
- Subjects device Global Impression of Effect will be documented.
- Adverse events will be documented.
- Device logs, for each Migraine treated episode, will be downloaded by the study team (from study cloud database or from the device) to ascertain eligible treatments. An eligible treatment is defined as:
 - treatment meeting the basic criteria (*i.e.*, no analgesics or other pain relief drugs or cannabis within 4 hours period before the treatment initiation; no more than 30 minutes passed from the start of the migraine episode; more than 48 pain free hours have passed since subject's previous Migraine episode; and subject did not wake up with a Migraine headache); and
 - with total stimulation time of at least 30 minutes of a "pass" session on the device log timeline, where pass is defined as a minimal stimulation of 2mA delivered).

The characteristics of each treatment will be indicated on the subject CRF.

At this point subject's participation in this study will be over. The subjects will continue receiving medical care as per local standard of care, but not within the clinical study. Adverse Events that are still ongoing will be followed per local standard of care, but not within the clinical study.

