8.6. Assessment of Efficacy

Efficacy parameters including Pain level, use of rescue medications/cannabis, presence and relief of most bothersome migraine-associated symptom other than headache will be documented during treatment at baseline, 1 hour, 2 hours and 24 hours.

These parameters will be documented by the subject using the diary (electronic or hard copy).

Treatment duration and intensity will be documented automatically in the device logs.

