10.1. Relivion Anticipated Adverse Events

Possible risks and adverse events that may be associated with the Relivion™ device are based on adverse events reports of similarity devices include, but are not limited to the following:

- Unpleasant sensation during treatment
- Scalp Numbness sensation during and after treatment
- Persistent tingling sensation after the treatment ends
- Pain
- Skin reaction (for example, irritation, lesion, burn) beneath the stimulation electrodes In this case, treatment should be temporarily discontinued.
- Redness of the skin under or around the electrodes. Skin redness usually disappears within several hours after treatment
- Sleepiness, fatigue or sleep disorders
- Sedative effect during or after treatment
- Dizziness during or after treatment
- Tension type headache after treatment

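### The safety endpoint has a 24-hour window, but the only itemised adverse-event enquiry covering home use is Visit 4, at most 80 days after Visit 2

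*Protocol*

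**What the plan says.** Section 4.2.3 of the protocol (repeated in the synopsis) gives the safety endpoint as "Rate of Adverse events related or unrelated to the study device [Time Frame: 24 hours post treatment initiation". It covers events of any relationship to the device and does not say which treatment starts the clock.

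The steps at which adverse events are itemised are few:

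- **Visit 2 (8.1.3):** "Adverse events occurring during the visit will be documented".
- **Self-practice at home (8.1.4):** two sessions; no adverse-event item.
- **Visit 3 (8.1.5):** checks of device logs and diary reporting, possibly remote. "Call will be documented and will be considered as remote study Visit 3". No adverse-event item.
- **Treatment period (8.1.6):** Table 1 schedules "Diary PRO at baseline, 1, 2 & 24 hr post treatment". The diary items listed are pain, the most bothersome symptom and rescue medication.
- **Visit 4 (8.1.7):** "Adverse events will be documented".

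The adverse-event row of Table 1 agrees, with marks at Visits 2 and 4 only. Sections 8.7 and 10 state more generally that events are collected from enrolment to study exit.

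The anticipated events in section 10.1 include sensations during treatment, numbness, tingling, sleepiness and dizziness. On redness the section adds: "Skin redness usually disappears within several hours after treatment".

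**The concern.** The endpoint looks at the day after a treatment, while the one itemised question about home use comes at the end of participation. Effects that last hours are the kind a subject is least likely to mention, or to place in time, weeks later and after several sessions. An incomplete count would make the device look better tolerated than it is, and the safety objective would rest on it.

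Two practical consequences follow. Visit 3 is the contact that clears a subject to start treating attacks after the first unsupervised use, yet its list does not prompt staff to ask what happened during that use. And the reporting deadlines in Table 2 run from the time the site learns of an event, so an event first mentioned at Visit 4 starts its clock late.

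**Working it through.** No sample-size or power figure is involved. The check is visit-window arithmetic and a comparison of sections.

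**1. Span of home use.** Table 1 sets Visit 2 at day 0 and Visit 4 after up to five episodes or at day 70+10. Section 8.1.5 agrees: "up to 5 migraine episodes within up to day 70+10 from Visit 2".

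- Nominal gap from Visit 2 to Visit 4: 70 days.
- Longest gap: 70 + 10 = 80 days.

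Section 7.2 counts the same 70+10 days from Visit 1. With a run-in of 28 to 38 days, that would leave 80 − 28 = 52 to 80 − 38 = 42 days after Visit 2. Sections 6.1, 8.1.5 and 8.1.6 and Table 1 all count from randomisation or Visit 2, so 80 days is the supported maximum.

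**2. Longest wait until the itemised question.**

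- Self-practice session soon after Visit 2: up to about 80 days.
- Attack treated straight after a Visit 3 on day 14: up to 80 − 14 = 66 days; longer, towards 80, if Visit 3 is earlier.
- Subjects who treat five attacks early reach Visit 4 sooner, so these are ceilings.

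**3. Home sessions to look back over.** 2 self-practice + up to 5 attacks = up to 7.

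**4. What exists at 24 hours.** A diary entry is already due at 24 ± 6 hours (8.1.6), that is, 18 to 30 hours after initiation. Its listed content has no safety item. Section 8.6 describes the content in the same way: "Efficacy parameters including Pain level, use of rescue medications/cannabis, presence and relief of most bothersome migraine-associated symptom other than headache will be documented". That section concerns efficacy, so its silence on safety carries little weight; the diary list in 8.1.6 is the better evidence.

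**5. How the safety variable is defined elsewhere.**

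| Place | Events | Time frame |
|---|---|---|
| Protocol 4.2.3 | All, related or not | 24 hours after treatment initiation |
| Protocol 11.1.4 | All, by severity and relationship | None stated |
| Protocol 11.7.5, primary safety variable | Device-related | Whole study |
| SAP section 3 | Treatment-related, serious, all | None stated |

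The 24-hour window appears in the endpoint definition but not in the analysis text.

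**6. Size of the under-count.** If a fraction c of affected subjects is recorded, a true incidence p is reported as c × p. With the same c in both arms, the difference between arms also shrinks by the factor c. Neither document gives a value for c or an expected incidence, so no figure follows.

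**The case against.** The strongest reply is that collection between visits is intended. Section 8.7 requires the type, incidence, severity and duration of events throughout the study, and section 10 repeats the Visit 2 to Visit 4 interval. The deadlines in Table 2 presuppose that sites hear of events between visits. Staff contact subjects periodically during the treatment period (8.1.6). Both documents are abridged, and the diary form, the subject instruction form and the adverse-event form are not shown. The schedule is the same in both arms. The SAP, which prevails over the protocol, does not use a 24-hour window.

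Much of this stands, and it rules out several stronger readings that a reader might infer:

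- *That home events rest wholly on recall at Visit 4.* Spontaneous reports and mentions during periodic contacts are possible. Visit 4 is the only itemised enquiry, not the only route.
- *That events cannot be dated.* Device logs record the date of each session, so an event with an onset date can be matched to one. Late recall makes onset less precise, not impossible to establish.
- *That the endpoint applies to the 24 hours after each treatment.* That is one reading; section 4.2.3 does not say which treatment it means.
- *That the comparison between arms is biased in one direction.* Nothing in the documents shows this.

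What does not stand is the claim that the general statements close the gap. The periodic contacts are described as reminders and possible retraining, and no section says that they ask about adverse events. Nor does the mismatch rest on a possibly damaged table: the visit lists and the diary list agree with Table 1.

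**Conclusion.** The point holds as a mismatch between the endpoint's time frame and the scheduled enquiry. For up to seven home sessions the plan itemises one adverse-event question, at most 80 days after Visit 2, while an existing diary entry at the endpoint's own time point does not list one. Under-reporting and imprecise timing of short-lived effects are likely. A reader may want to put a percentage on the loss, but any capture rate would be invented. Primary efficacy is unaffected.

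The conclusion assumes that the diary, forms and contact scripts that are not shown add no adverse-event question beyond what the abridged protocol lists. If they do, the gap narrows to a failure to say so in the schedule.

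The safety definitions need reconciling in either case: a 24-hour all-event endpoint, a device-related whole-study variable and a SAP list without a time frame are three different quantities.

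**What to change.** 1. Add one question to the existing 24-hour diary entry: any new symptom or skin reaction since this treatment, yes or no, with onset time and free text for site follow-up. Onset time is needed because the entry may be made at 18 to 30 hours.
2. Mark adverse events at Visit 3 in Table 1 and add the item to section 8.1.5. This covers self-practice, for which Table 1 schedules no 24-hour diary.
3. State one safety variable, with its events, time frame and reference treatment, and use it in protocol sections 4.2.3, 11.1.4 and 11.7.5 and SAP section 3. Keep Visit 4 as a catch-up enquiry.
4. The SAP introduction says that enrolment stopped on 2 July 2020. For subjects whose data collection is complete, items 1 and 2 cannot recover past events. The report should then state how and when adverse events were elicited and dated, and list this as a limitation.

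The cost is one diary question, one table mark, one line of protocol text and a definition edit; the diary entry and the Visit 3 contact already exist. The downside is that the reported adverse-event rate will probably rise in both arms.

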4.2.4. Exploratory Endpoints

1. Proportion of subjects reporting freedom from their MBS other than a headache, 2 hours post-treatment initiation (if rescue therapy was not used), in their first eligible treated migraine attack.
2. Proportion of subjects who are pain free at 1-hour post treatment initiation (if rescue therapy was not used), in their first eligible treated migraine attack.
3. Proportion of subjects rating the subjects positive (score of 4 or 5) Global Impression of Effect of study device at the end of the study, defined as satisfied or very satisfied using a simple Likert-type scale whereas 1 = Very dissatisfied, 2 = dissatisfied, 3 = unsure, 4 = satisfied, 5 = Very satisfied.
4. Proportion of subjects reporting 2-24h headache relief, defined as headache relief at 2 hours without rescue medications, then no moderate to severe headache in the next 22 hours, and no use of rescue medication or additional stimulation.

5. Product Description

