8.5. Medication Compliance

While using the Relivion™ the subject will be asked to refrain from taking rescue medications/cannabis in the 4 hours prior to and 2 hours following each treatment. Subject will ascertain he/she did not consume any rescue medications/cannabis in the 4 hours prior to study treatment initiation. During each study treatment and up to 24 hours afterwards subjects will document any rescue medication/cannabis intake. PRO data of subjects who consumed rescue medications/cannabis will not be considered for the analysis of the related treatment time point.

 Neurolief Brain Innovation	THE RIME STUDY: ABRIDGED CLINICAL INVESTIGATION PLAN	Doc No.: CL-CIP-001 Abridged Ref Rev: REV.2 / 11JUN2019 Pg. 29 of 41
--	---	---

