Secondary efficacy endpoints include:

1. Proportion of subjects reporting improvement in their most bothersome migraine-associated symptom (MBS) other than a headache, 2 hours post-treatment initiation (if rescue therapy was not used), in their first eligible

treated migraine attack. MBS may be nausea, photophobia, phonophobia as defined by each subject prior to beginning of the treatment.

2. Proportion of subjects reporting reduction of migraine headache pain 1-hour post treatment initiation (if rescue therapy was not used), from severe or moderate to mild or no pain, or from mild to no pain, in their first eligible treated migraine attack.
3. Proportion of subjects who are pain free at 2 hours post treatment initiation (if rescue therapy was not used), in their first eligible treated migraine attack.

2.3

Additional efficacy endpoints

1. Proportion of subjects reporting freedom from their MBS other than a headache, 2 hours post-treatment initiation (if rescue therapy was not used), in their first eligible treated migraine attack.
2. Proportion of subjects who are pain free at 1-hour post treatment initiation (if rescue therapy was not used), in their first eligible treated migraine attack.
3. Proportion of subjects rating the subjects positive (score of 4 or 5) Global Impression of Effect of study device at the end of the study, defined as satisfied or very satisfied using a simple Likert-type scale whereas 1 = Very dissatisfied, 2 = dissatisfied, 3 = unsure, 4 = satisfied, 5 = Very satisfied.
4. Proportion of subjects reporting 2-24h headache relief, defined as headache relief at 2 hours without rescue medications, then no moderate to severe headache in the next 22 hours, and no use of rescue medication or additional stimulation.

Additional efficacy analyses that will be performed

1. Proportion of subjects reporting improvement in their MBS other than a headache AND reduction in their pain level, 1 and 2 hours post-treatment initiation (if rescue therapy was not used), in their first eligible treated migraine attack.
2. Proportion of subjects reporting freedom from their MBS other than a headache AND pain free, 1 and 2 hours post-treatment initiation (if rescue therapy was not used), in their first eligible treated migraine attack.
3. Rescue medicine usage.
4. Proportion of subjects who had pain relief in at least 50% of their eligible treated attacks at each timepoint.

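### The 2-24 h relief endpoint requires 22 hours without moderate or severe headache, but the described diary cannot show this: untreated relapses that subside before the 24-h score go unseen

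*Protocol*

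**What the plan says.** Exploratory endpoint 4 (protocol synopsis and section 4.2.4) needs relief at 2 hours without rescue, "then no moderate to severe headache in the next 22 hours, and no use of rescue medication or additional stimulation". SAP section 2.3, item 4, keeps the definition. It opens with "Proportion of subjects reporting 2-24h headache relief, defined as headache relief at 2 hours without rescue medications" and carries over the same interval condition: "then no moderate to severe headache in the next 22 hours". Where the two documents differ the SAP prevails, but it adds no rule for deriving the interval.

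The recording schedule is given in three places in the protocol:

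- Table 1 (section 8.1): "Diary PRO at baseline, 1, 2 & 24 hr post treatment".
- Section 8.1.6: "Pain according to a 4 points scale (0=no pain, 1=Mild pain, 2=Moderate pain, 3=Severe pain) at 1 and 2 hours", each ±30 minutes, and again at 24 hours ± "6 hours post initiation of treatment".
- Section 8.6: efficacy parameters, pain level among them, "will be documented during treatment at baseline, 1 hour, 2 hours and 24 hours".

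The other two components are followed over time. Section 8.5 states: "During each study treatment and up to 24 hours afterwards subjects will document any rescue medication/cannabis intake". Section 8.6 has treatment duration and intensity written automatically to the device logs.

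Section 11.1.3 codes each exploratory endpoint 1 for a responder and 0 otherwise. Section 8.5, however, also leaves the diary data of rescue users out of the analysis of the related time point.

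**The concern.** The definition is a statement about an interval, while the pain data described are scores at single times. Between the 2-h and the 24-h score there is no rating, no worst-pain item and no recurrence question. The criterion of no moderate or severe headache over 22 hours therefore rests on one score near the end of the period.

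A subject whose headache returns, is left untreated and fades before that score looks the same in the data as one who stayed well throughout. If the endpoint is derived in the obvious way, both are coded 1. The reported proportion would then be too high for the definition printed above it, and readers would take it as evidence of relief that lasted.

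The protocol's own background makes such relapses plausible. Section 3.1 puts a migraine headache at 4 to 72 hours, so a short recurrence fits inside the gap. Section 8.1.6 also tells subjects not to use the device until 48 pain-free hours have passed since the previous episode, so the additional-stimulation component may pick up few recurrences.

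**Working it through.** The plan gives no figure for this endpoint, so there is nothing to reproduce. The check has three parts.

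**1. Each component against what is recorded**

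| Component | Recorded as | Covers 2 to 24 h? |
|---|---|---|
| No rescue medication | intake documented up to 24 h after treatment (8.5) | yes |
| No additional stimulation | device logs (8.6) | yes |
| No moderate or severe headache | scores at 2 h and 24 h (8.1, 8.1.6, 8.6) | only at the two ends |

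A relapse is missed only if all of the following hold: it is not treated with rescue, it is not restimulated, and pain is none or mild at the 24-h score.

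**2. Length of the gap between the two scores**

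- Nominal: 24 − 2 = 22 h.
- Shortest within the windows: 18 − 2.5 = 15.5 h.
- Longest within the windows: 30 − 1.5 = 28.5 h.

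A last score at 18 h says nothing about the remaining 24 − 18 = 6 h of the period. A last score at 30 h can fail a subject for pain that began up to 6 h after the period ended. A momentary score does not cover the interval wherever it falls in the window.

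**3. Possible size**

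The 2-h relief rates are the planning values of protocol section 11.3: 45% active and 25% sham. All other inputs are assumptions; none comes from the documents.

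- r, share of 2-h responders who relapse to moderate or severe: 20% to 40%.
- u, share of relapses left untreated: 20% to 50%.
- v, share of those resolved by the 24-h score: 50%.

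Wrongly counted share of the arm = relief rate × r × u × v.

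- Active, low: 0.45 × 0.20 × 0.20 × 0.50 = 0.009, or 0.9 points.
- Active, high: 0.45 × 0.40 × 0.50 × 0.50 = 0.045, or 4.5 points.
- Sham, low: 0.25 × 0.20 × 0.20 × 0.50 = 0.005, or 0.5 points.
- Sham, high: 0.25 × 0.40 × 0.50 × 0.50 = 0.025, or 2.5 points.

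With the same relapse behaviour in both arms, the difference between arms shifts by 0.9 − 0.5 = 0.4 to 4.5 − 2.5 = 2.0 points. If relapse behaviour differs between arms, the shift may go either way.

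The result depends heavily on the assumptions. Take r = 10% to 40%, u = 10% to 70% and v = 60% to 100%. The missed share of 2-h responders then runs from 0.10 × 0.10 × 0.60 = 0.6% to 0.40 × 0.70 × 1.00 = 28%. That is 0.27 to 12.6 points in the active arm and 0.15 to 7.0 in the sham arm.

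The SAP introduction reports 109 subjects with primary-endpoint data, about 54.5 per arm if evenly split. On the narrower range the active arm would hold 54.5 × 0.009 = 0.5 to 54.5 × 0.045 = 2.5 misclassified subjects.

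**The case against.** The case for leaving this alone has several parts.

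- **Most relapses may be caught.** A reader might infer that every relapse between 2 and 24 hours passes as relief. The documents do not support that. Subjects are asked to avoid rescue medication only for the first 2 hours, later intake is documented, stimulation is logged, and pain still moderate or severe at the 24-h score fails. This stands, and it confines the problem to untreated relapses that subside.
- **It is not the only durability measure.** SAP 2.3, additional analyses 10 and 11, reports relief and pain freedom at 24 hours in subjects with moderate or severe baseline pain. This stands too. Those are assessments at a single time and claim nothing about the interval; endpoint 4 is the one that does.
- **The diary is not shown.** Both documents are abridged, so the lack of a look-back item is inferred from silence. How the endpoint would be coded is likewise inferred, since no derivation rule is given. This stands as a caveat. It does not excuse the missing rule, because the SAP would need to name such an item if it existed.
- **The size rests on assumption.** It does. Only the planning relief rates come from the documents, and misclassification in both arms partly cancels in the comparison.
- **Little depends on it.** The endpoint is exploratory, outside the testing hierarchy, and touches neither sample size nor alpha. That limits the importance of the point, but a tested comparison would still be published under this definition.

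**Conclusion.** The point holds in a limited form. As described, the data can show relief at 2 hours, no or mild pain at about 24 hours, and no recorded rescue or restimulation. They cannot show that no moderate or severe headache occurred in between. The error goes one way within each arm: untreated relapses that subside before the last score raise the apparent rate of sustained relief. A late score can also fail a subject for pain arising after the period.

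The size is unknown. The figures of 0.9 to 4.5 points (active) and 0.5 to 2.5 points (sham) illustrate assumed relapse rates and the planning relief rates; they are not estimates. It would be going too far to conclude that the comparison is biased in favour of the active device, since the direction depends on relapse behaviour in each arm, which the documents do not give. Nor is the endpoint unusable: two of its components are measured over the interval and the third at both ends. The primary result, the secondary endpoints and the success criterion are unaffected.

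**What to change.** Change SAP section 2.3, item 4, before unblinding. The SAP states that the data are still blinded and unanalysed, so this can be done cleanly.

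1. Redefine and relabel the endpoint as pain relief at 2 hours and no or mild pain at the 24-h score, with no rescue medication or additional stimulation recorded in between. Do not report it as absence of moderate or severe headache over 22 hours. If the full diary does hold a look-back item, name it and derive the endpoint from it instead.
2. State how scores taken between 18 and 30 hours are handled, and report the distribution of their timing by arm.
3. Reconcile protocol section 8.5 with sections 4.2.4 and 11.1.3. Under the first, rescue users' diary data are left out at the related time point; under the others, rescue users count as non-responders. If 8.5 were applied here, treated relapses could drop out of the denominator instead of failing.

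Enrolment stopped on 02 July 2020, before the SAP of 31 August 2020, so a new diary question would come too late for these data. For any further data collection, one question in the 24-h diary on whether the headache was moderate or severe at any time since the 2-h report would close the gap.

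The cost is a few lines of SAP text and a narrower durability claim.
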